# 5.3 Interventions

Following consent and randomisation at the Preoperative Assessment Clinic (POAC) visit one group will receive the current pre-operative carbohydrate solution, *Preload*® (a maltodextrin solution), and the other group will receive *Generation UCAN* (a hydrothermally modified starch solution) to take home.

In both cases these will be dispensed as a powder in a clear plastic zip lock bag to ensure blinding of the patient (the research team will have decanted the appropriate dose of each supplement into these bags and will be aware of the allocated intervention). This will be a single sachet, in the case of *Preload®*, and an equivalent weighed and measured volume from a large tub, in the case of Generation UCAN. Both groups will be instructed to reconstitute the powder provided in 400mls of water on the day of surgery, and consume it between two and three hours before surgery, as per standard practice in the ERP.

Both groups will also be instructed to consume approximately 500mls (1 pint) of water with their evening meal the evening before surgery to remain well hydrated.

The Control group will receive 47.5g of carbohydrate in the form of Preload®.

The Intervention group will receive 56.55g of flavoured Generation UCAN (providing 47.5g of carbohydrate).

All other aspects of patient care will be standardized as per our ERP (see Appendices).

#### 5.4 OUTCOMES

## PRIMARY OUTCOME

 Change in insulin resistance from baseline on POD 1 measured using a technique called HOMA (see Appendices), which utilises serial fasting blood glucose and insulin measurements.

#### **SECONDARY OUTCOMES**

- Change in insulin resistance from baseline on POD 2 and POD 3 measured using a technique called HOMA, which utilises serial fasting blood glucose and insulin measurements.
- Stress response following surgery, measured by sampling cortisol levels preoperatively, at the end of surgery, and at 24 hours post-operatively and the inflammatory response measured by CRP levels preoperatively, and on POD 1,2 and 3.
- Ultrasound measurement of gastric volume pre-operatively (see Appendices for technique)
- Recovery profile including:
  - PQRS (see Appendices) score measured pre-operatively, at 2 hours after surgery, POD 3 and POD 7;
  - Muscle strength measured using a grip strength dynamometer pre-operatively, twice daily (morning and afternoon) on POD 1, 2 and 3, and then once daily on alternate days thereafter until discharge (the patient's dominant hand will be used for this measurement, and the best out of three consecutive strengths will be used with mean values analysed);
  - Time to surgical fitness for discharge (see Appendices for criteria) measured in hours (date and time of fitness for surgical discharge is recorded in the ERP database).
- Morbidity measured using the POMS score on POD 2 and POD 5 (see Appendices).
- PONV VAS score on POD 1.
- Sensations of thirst & hunger VAS score immediately pre-operatively and on POD 1.
- Caloric intake POD 1 and 2.
- Ambulation time POD 1 and 2.
- Adverse events i.e. aspiration and hypo- or hyperglycaemia (these are the only relevant safety assessments for these interventions) will be assessed on the operative day for the former & up to the end of POD 1 for the latter.
- Cost analysis: difference in cost between doses of Pre-Load & Generation UCAN and costs of respective hospital and critical care lengths of stay.

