## 7. METHODS: DATA COLLECTION, MANAGEMENT, AND ANALYSIS

#### 7.1 Data collection methods

Data will be collected from patient notes (pre-operative assessment booklet, anaesthetic chart, operative note, notes made post-operatively) and the ERP Database. The research team will perform the blood sampling and record the measured results as described and collect the VAS scores.

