## POST-OPERATIVE DATA COLLECTION

- POSSUM score from ERP Database
- Blood samples:
  - Fasting insulin (3 samples to be taken at 5 minute intervals and glucose on the morning of POD 1, 2 and 3
  - Cortisol (at end of operation and at 24 hours)
  - o CRP (POD 1 and 3)
- PQRS score Theatre Recovery, POD 3 and POD 7.
- PONV and Thirst and hunger sensation VAS scores on POD 1.
- POMS score on POD 2 and 5
- Hand grip strength measurement twice daily on POD 1, 2 & 3 and then alternate days until discharge
- Calories intake POD1 and POD2
- Ambulation time (minutes) POD1 and POD2
- MUAC POD5 or Day of Discharge if earlier
- Adverse Events up to end POD 1.
- Date and time reached surgical fitness for discharge and actual discharge obtained from ERP Database

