#### **END OF TRIAL**

The end of the trial will be when the final patient has been discharged from hospital, at which point the 'declaration of end of trial' form will be submitted to the REC, as required.

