## METHODS FOR ANY ADDITIONAL ANALYSES (EG, SUBGROUP AND ADJUSTED ANALYSES)

If differences are observed in baseline demographic and/or clinical variables prognostic of outcome, then the analysis of the primary and secondary outcomes will be adjusted for using regression-based analysis appropriate to the type of outcome variable. The trial statistician will describe details of sub-group analysis in the statistical analysis plan if possible.

DEFINITION OF ANALYSIS POPULATION RELATING TO PROTOCOL NON-ADHERENCE (E.G., AS RANDOMISED ANALYSIS), AND ANY STATISTICAL METHODS TO HANDLE MISSING DATA (EG, MULTIPLE IMPUTATION) All analysis will be performed according to the intention to treat principle. The primary analysis will be based only on data obtained; sensitivity analysis will explore sensitivity to assumptions around missing data and details will be included in the statistical analysis plan devised by the trial statistician.

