## REPORTING PROCEDURES

All patients undergoing this trial are having major abdominal surgery and there is a recognised high risk of morbidity, therefore they are at risk of frequent AE. These events are largely as a result of a patient's medical condition and consequences of major surgery and may not be related to the trial. Consequently any AEs occurring as a result of patient's condition will not be reported. All other AEs that occur during the trial period from treatment to hospital discharge must be recorded in the patient notes. Any AE will be reported to the CI directly. The CI will facilitate any local monitoring by the R&D quality manager, REC review and provide access to source data as required. Following any monitoring a report will be provided which will summarise the visit and documents, along with any findings. The CI will be responsible for ensuring that all findings are addressed appropriately. Additional monitoring will be scheduled where there is evidence of suspicion of non-compliance with the Trial protocol.

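### PQRS at POD 7 and POMS at POD 5 are compared between arms, but no collection after discharge is described, so patients who go home earlier may be missing because they recovered

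*Protocol*

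**What the plan says.** Among the secondary outcomes in Section 5.4, the PQRS is a "score measured pre-operatively, at 2 hours after surgery, POD 3 and POD 7". The list also has "Morbidity measured using the POMS score on POD 2 and POD 5". The post-operative collection list in Section 7.1 repeats the schedule ("PQRS score Theatre Recovery, POD 3 and POD 7") without saying how a score is obtained from someone who has gone home. The same list gives the arm-circumference measurement a rule for early discharge: "MUAC POD5 or Day of Discharge if earlier". POMS and PQRS have none.

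On sources, Section 7.1 states: "Data will be collected from patient notes (pre-operative assessment booklet, anaesthetic chart, operative note, notes made post-operatively) and the ERP Database". It adds blood sampling and VAS scores by the research team. Section 8.2 records adverse events only up to discharge: "All other AEs that occur during the trial period from treatment to hospital discharge must be recorded in the patient notes". Under End of Trial in Section 7.2: "The end of the trial will be when the final patient has been discharged from hospital". The timeline in Section 5.5 places POD 5 and POD 7 ahead of the discharge column.

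Section 7.3 names the PQRS for a t-test or Mann-Whitney comparison and assigns categorical secondary outcomes to the chi-square test. On missing data it says "The primary analysis will be based only on data obtained", invokes intention to treat, and leaves sensitivity analyses to the statistical analysis plan.

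**The concern.** Whether a patient is in hospital on POD 5 or POD 7 is decided after randomisation. Section 4.1 hypothesises that the starch reduces morbidity and thereby shortens the time to being fit for discharge, and Section 5.4 makes that time an outcome. If scores exist only for inpatients, each arm is represented by its slower-recovering patients, and the cut may fall at a different point in each arm. The comparison is then no longer one of randomised groups, despite the intention-to-treat statement.

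The selection is also tied to what the scales measure. The discharge criteria in the appendix require tolerated diet and pain controlled by oral analgesia. POMS scores failure to tolerate enteral diet and the need for parenteral opioids or regional analgesia. PQRS includes pain, nausea and vomiting.

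At stake are the last planned readings of morbidity and of quality of recovery.

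**Working it through.** **The plan's own figure.** Section 5.6 gives a difference of 15%, SD 16%, two-sided 0.05 and 80% power. n = 2(1.96 + 0.84)² × (16/15)² = 17.9, so 18 per arm; 18/0.9 = 20, as stated. (The exact t-test gives 19, and 19/0.9 = 21.1.) The sample size is not in dispute. It supplies the 20 per arm used below.

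**How many scores would exist.** Length of stay is not in the protocol, so the share f still in hospital on POD 7 is an assumption. If only inpatients are scored, the expected number per arm is 20f. The detectable difference is for a two-sample t-test with 80% power at two-sided 0.05.

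| Assumed f at POD 7 | Scores per arm | Detectable difference (SD) |
|---|---|---|
| 10% | 2 | not computed |
| 20% | 4 | 2.38 |
| 30% | 6 | 1.80 |
| 50% | 10 | 1.32 |
| 70% | 14 | 1.10 |
| 100% | 20 | 0.91 |

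The chance that at least one arm has fewer than two scores is 1 − [1 − P(X ≤ 1)]², with X binomial(20, f). At f = 10%, P(X ≤ 1) = 0.392, giving 63%. At f = 20%, P(X ≤ 1) = 0.069, giving 13%.

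The same arithmetic applies to POMS on POD 5 with its own f, which is no lower than at POD 7 unless patients are readmitted.

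**Selection, as an illustration.** Assume that recovery is normally distributed with SD 1, that treatment improves both recovery and the score by d = 0.5 SD, that patients below a common recovery threshold c remain in hospital, and that score and recovery correlate at ρ within arm. With m(x) = φ(x)/Φ(x), the difference seen among inpatients is

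d − ρ[m(c − d) − m(c)].

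For 20% of controls in hospital, c = −0.84, m(c) = 1.40 and m(c − d) = 1.80. With ρ = 0.5 the observed difference is 0.5 − 0.5 × 0.40 = 0.30. With ρ = 0.8 it is 0.5 − 0.8 × 0.40 = 0.18. The treated share in hospital is then 9%.

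Across 20-50% of controls in hospital and ρ from 0.5 to 0.8, simulation of this model gives observed differences of 0.18 to 0.33 SD against a true 0.5 SD. The observed control mean lies 0.40 to 1.12 SD below the mean of the whole control arm. Under these assumptions the comparison is pulled by 0.17 to 0.32 SD against the faster-recovering arm.

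**The case against.** The strongest reply is that the protocol is silent on contact after discharge rather than excluding it. Section 5.4 limits grip strength to the period before discharge but sets no such limit on PQRS or POMS, so these could be read as due wherever the patient is. Sections 7.2 and 9.4 keep identifiers for follow-up. This stands in part: the defect is an undescribed mode of collection, and nothing shows an intention to leave discharged patients out. But those sections set no procedure for either scale, and the only telephone contact described is during recruitment.

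A reader might also infer that the protocol expects most patients home before POD 5. It does not say so. The arm-circumference rule allows for early discharge without predicting it, Section 5.7 prefers patients needing a higher level of care, and no length of stay is given. If most patients stay beyond POD 7, the problem is small.

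It is further tempting to argue that the better arm will come out looking worse. Counts can be chosen to produce a reversal, but nothing in the protocol supports any particular set, and the illustration above shows attenuation. Nor is there a stated day-by-day comparison of grip strength after POD 3 to criticise.

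Missing-data handling may properly be left to the statistical analysis plan, and a POMS scoring rule could be placed there. That plan cannot, however, recover POD 7 PQRS scores that were never collected. The sentence on data obtained could also be read as covering only the primary outcome. The named tests would still use whatever scores exist.

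Finally, the end-of-trial definition can cut off POD 7 only for the last patient or few.

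**Conclusion.** The point holds as a gap in the data-collection design that should be closed. Followed as written, the protocol may obtain PQRS on POD 7 and POMS on POD 5 only from inpatients, and would then compare arms on a subset shaped by recovery after randomisation. The case is firmest for PQRS on POD 7. POMS can be settled by a scoring rule, but the protocol states none.

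The size is uncertain. At an assumed 10-50% still in hospital on POD 7, about 2-10 of 20 per arm contribute. Which arm is penalised, and by how much, depends on discharge timing in each arm, which the protocol does not give. The attenuation from 0.5 SD to 0.18-0.33 SD rests wholly on assumed values. A sign reversal, or a claim that these outcomes will exist mainly for inpatients, goes beyond the protocol. Only secondary outcomes at two late time points are affected; the primary outcome on POD 1 is not touched.

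**What to change.** **PQRS on POD 7.** Either (a) telephone discharged patients in both arms on POD 7 for the domains that can be asked remotely, and compare arms on those domains only; or (b) make POD 3 the last compared PQRS and report POD 7 descriptively. Option (a) costs one short call per discharged patient, at most 40 in all, and loses the physiological domain at POD 7. The protocol does not say which domains may be given by telephone, so this must be confirmed from the instrument's own guidance. Option (b) needs only wording but gives up the late comparison.

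**POMS on POD 5.** Keep all randomised patients in the denominator. Prespecify that a patient discharged alive before POD 5 counts as free of POMS-defined morbidity, and label this as a convention. Its weakness is that the discharge criteria do not rule out every POMS item: a patient may go home on oral antibiotics or with a catheter. The same call could ask about these, with two days' recall.

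**Grip strength after POD 3.** Treat as descriptive only.

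**End of trial.** Define it as the later of the last discharge and the last POD 7 assessment. If POD 7 is dropped, the present definition can stand.

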The rationale for this pilot study is that HPMS drinks given pre-operatively may result in a further reduction in insulin resistance post-operatively compared with standard maltodextrin containing carbohydrate drinks due to a longer duration of action, a greater reduction in peak glucose concentration, a greater reduction in post-operative blood insulin levels and a greater lipid oxidation. This in turn may lead may lead to a greater reduction muscle loss and morbidity, specifically infectious complications, and in turn time to fitness for hospital discharge.

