#### 5.6 Sample Size

The standard deviation for insulin resistance data was obtained from a previous study of pre-operative carbohydrate treatment in total hip replacement surgery (Soop 2001). Twenty patients in each group are needed based on 80% power for a two-sample t-test, detecting a minimal important difference of 15% in change of insulin resistance on the first postoperative day from baseline, with a standard deviation of 16% and a two-tailed significance level of 0.05. A minimal important difference of 25% was used in a previous study comparing pre-operative carbohydrate treatment with a placebo group for patients who had total hip replacement (Soop 2004) . In this study two carbohydrate drinks are being compared, PreLoad with Generation UCAN. Therefore, a smaller minimal important difference of 15% was deemed appropriate. This sample size calculation allows for 10% attrition.

\*\* Measured twice a day first three postoperative days then alternate days until discharge from hospital.

\*\*\*The baseline HOMA to be done on either of these 2 visits as long as the patient is fasted.

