#### 7.3 STATISTICAL METHODS

#### STATISTICAL METHODS FOR ANALYSING PRIMARY AND SECONDARY OUTCOMES

Baseline demographic and clinical variables will be reported for the two groups using summary statistics. Categorical variables will be reported using frequencies and percentages. Quantitative variables will be reported using either the mean and standard deviation or the median and interquartile range depending on the skewness of the data

In terms of the primary outcome, the mean difference in change of insulin resistance from baseline to POD 1 will be compared using either the Independent Samples T-Test or Mann-Whitney U Test. This will depend on the skewness of the data distribution.

Between-group comparisons of quantitative secondary outcomes including change of insulin resistance from baseline to POD 3, the PQRS score and time to surgical fitness will made using either the Independent Samples T-Test or Mann-Whitney U Test, depending on the skewness of the distribution of the data. Categorical secondary outcomes will be compared between groups using the Chi-square test.

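### Grip strength is measured until discharge and analysed as mean values with no common end day, so any comparison using readings after POD 3 depends on length of stay

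*Protocol*

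**What the plan says.** Section 5.4 (secondary outcomes) lists muscle strength by dynamometer before surgery, "twice daily (morning and afternoon) on POD 1, 2 and 3", "and then once daily on alternate days thereafter until discharge". For the summary it states that "the best out of three consecutive strengths will be used with mean values analysed".

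The same schedule appears twice more. The data-collection list in section 7.1 has "Hand grip strength measurement twice daily on POD 1, 2 & 3 and then alternate days until discharge". The footnote to the participant timeline, which stands beneath section 5.6 in the text, has "Measured twice a day first three postoperative days then alternate days until discharge from hospital". The three places agree, and none gives an end day common to all patients.

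Section 7.3 says that "Between-group comparisons of quantitative secondary outcomes" will use an independent-samples t-test or a Mann-Whitney test, depending on skewness. It names no repeated-measures method.

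Discharge timing is itself an outcome: section 5.4 lists "Time to surgical fitness for discharge (see Appendices for criteria) measured in hours". The rationale in section 4.1 says the modified starch may reduce muscle loss and morbidity, "specifically infectious complications, and in turn time to fitness for hospital discharge".

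**The concern.** The fixed part of the schedule gives every patient who stays through POD 3 the same six sessions. The open part adds sessions only for those who stay longer. The protocol does not say whether these extra sessions enter the between-arm comparison. There are two ways in which they could.

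- **Pooled patient mean.** All of a patient's sessions are averaged into one number. Two patients with the same daily strength then get different values if they go home on different days.
- **Daily group mean.** Each day is compared separately. From POD 5 onward, each arm then contains only the patients still in hospital, who may be differently selected in the two arms.

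Either way, the readings used depend on an event after randomisation that the drink may affect. If it does, the grip comparison mixes strength with length of stay, and a difference in recovery could be partly hidden or otherwise altered.

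**Working it through.** **The plan's own figure.** The protocol states no figure for grip strength. Its only design figure, 20 per group, belongs to the primary outcome. It reproduces: a difference of 15 with SD 16, two-sided 5% and 80% power gives 18 per group by the normal approximation, and 18/0.9 = 20. This point does not touch it.

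**Step 1: sessions by day of discharge.** The schedule comes from section 5.4. Two assumptions are added: alternate days are POD 5, 7, 9 and 11, and sessions due on the day of discharge are done.

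| Discharge | Sessions | Mean session day | Share after POD 3 |
|---|---|---|---|
| POD 3 or 4 | 6 | (1+1+2+2+3+3)/6 = 12/6 = 2.00 | 0% |
| POD 5 or 6 | 7 | (12+5)/7 = 17/7 = 2.43 | 1/7 = 14% |
| POD 7 or 8 | 8 | (17+7)/8 = 24/8 = 3.00 | 2/8 = 25% |
| POD 9 or 10 | 9 | (24+9)/9 = 33/9 = 3.67 | 3/9 = 33% |
| POD 11 | 10 | (33+11)/10 = 44/10 = 4.40 | 4/10 = 40% |

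This step needs no assumption about recovery. It shows that a pooled mean refers to a different average day for different patients.

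**Step 2: two patients with the same recovery.** Assume grip is 85% of baseline on POD 1, rises linearly by g points a day, and stops at 100%. The pooled means for discharge on POD 4 and POD 9 are:

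- g = 1: 86.0 and 87.7, a gap of 1.7
- g = 2: 87.0 and 90.2, a gap of 3.2
- g = 3: 88.0 and 91.7, a gap of 3.7

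The ceiling of 100% limits the last two gaps. Without it the gap would be (3.67 − 2.00) × g.

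**Step 3: two patients with different recovery.** The fast patient gains 3 points a day and goes home on POD 4, with a mean of 85 + 3 × (2.00 − 1) = 88.0. The slow patient goes home on POD 9.

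- Slow at 1.5 a day: pooled mean 85 + 1.5 × 2.67 = 89.0, so the fast patient looks 1.0 worse. Over POD 1 to 3 the values are 88.0 and 86.5, so the fast patient is 1.5 better. The order reverses.
- Slow at 0.5 a day: pooled mean 85 + 0.5 × 2.67 = 86.3, so the fast patient is 1.7 better. Over POD 1 to 3 the values are 88.0 and 85.5, a gap of 2.5. The difference only shrinks.

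The direction between unlike patients is therefore not fixed.

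**Step 4: two arms.** This is a simulation with 20,000 patients per arm. Assumptions: mean start 85 (SD 8), slope SD 0.7 points a day, measurement SD 3, and stay of about 3 + 6/slope days (SD 1), limited to 3 to 15 days.

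| Slopes (points/day) | Mean stay (days) | Difference, POD 1–3 mean | Difference, pooled mean |
|---|---|---|---|
| 2 and 2 | 6.5 and 6.5 | −0.03 | −0.03 |
| 2 and 3 | 6.5 and 5.2 | 0.94 | 0.76 |
| 1.5 and 3 | 7.9 and 5.1 | 1.63 | 1.32 |

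Attenuation is (0.94 − 0.76)/0.94 = 19% and (1.63 − 1.32)/1.63 = 19%. With equal slopes the pooled mean adds nothing to the difference between arms.

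**Step 5: does a POD 1 to 3 mean cure it?** Not fully. A patient who goes home on the afternoon of POD 2 with three sessions has a mean session day of (1+1+2)/3 = 1.33 instead of 2.00. A single POD 1 to 3 mean still depends on stay for such patients. A comparison by day does not blend the days.

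**The case against.** The strongest reply is that no sentence pools all of a patient's sessions. The remark about mean values follows the best-of-three rule and a morning-and-afternoon schedule, so a daily average or a group mean per day fits just as well. The tests in section 7.3 need one value per patient per comparison, not one per patient overall. The same section applies them to a recovery score taken at several times. As far as the timeline table can be read, it lists grip by day. All of this stands: pooling is one reading among several. It does not clear the plan, because daily means after POD 3 rest on patients still in hospital. Only a restriction to POD 1 to 3 avoids the dependence, and the protocol does not state one.

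A second reply is that such detail belongs in the SAP, which is not at hand. The SAP may well settle it. But the protocol itself fixes an open-ended window and a summary measure for this outcome. What section 7.3 expressly leaves to the SAP is subgroup detail and sensitivity to missing data.

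A third reply is that the harm is hypothetical. A reader might infer that slower patients gain later, better days and that the comparison is therefore tilted towards the arm that stays longer. The documents do not support that. They contain no grip data, patients kept in by complications may have weaker late readings, and the rationale says only that the drink may shorten time to fitness. The gaps in step 2 compare two hypothetical patients, not two arms.

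**Conclusion.** The point holds in a limited form. The protocol ties the grip measurement window to discharge, sets no common end day and leaves the averaging undefined. If readings after POD 3 are used in the between-arm comparison, it depends on a post-randomisation outcome that the drink may affect.

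It would go too far to say that the comparison is biased, or in which direction. That would need three things the documents do not give: that late readings are used, how grip recovers, and that stay differs by arm. The distortion is nil if the arms recover equally. It is about 19%, or 0.2 to 0.3 points of baseline grip, in the two scenarios with assumed slopes and with stay tied to recovery. Only a secondary outcome of a pilot trial is affected; the primary outcome and sample size are not. This is a minor point, worth settling because doing so is cheap.

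**What to change.** In sections 5.4 and 7.3, define the grip outcome as follows:

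- Take the best of three attempts at each session and average morning and afternoon within the day, on POD 1, 2 and 3.
- Compare the arms by day, or in a repeated-measures model over POD 1 to 3, with the pre-operative reading as baseline. Give the number measured each day, so that patients discharged before POD 3 are handled openly and not absorbed into a shorter mean.
- Report readings after POD 3 descriptively by arm and day, with the number still in hospital.

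This takes a few sentences and no new measurement. The cost is that the later alternate-day readings leave the between-arm test.

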#### 5.7 RECRUITMENT

The colorectal specialist nurses will be asked to forward details of patients listed for eligible surgery following each Colorectal Cancer MDT Meeting. All of the surgeons who are part of this group, along with the Waiting List Clerks who book the operation dates, the Pre-operative Assessment Clinic staff (the CI also undertakes weekly Cardiopulmonary Exercise Testing Clinics in this area) and the Enhanced Recovery Nurse will all be aware of the study eligibility criteria and inform the research team as early as possible regarding such patients.

Patients requiring admission to a higher level of care and therefore arterial line monitoring will be preferred due to the ease of blood sampling.

Local data for the past four years indicates an average of 50 eligible patients per year at the Royal Blackburn Hospital. The Royal Surrey County Hospital has a higher volume of eligible patients. Due to the non-invasive nature of the intervention and experience with current interventional RCT at both centres in a similar study population a high approach to consent ratio would be expected. Hence recruitment of 40 patients (20 patients per centre) is feasible in 6 months.

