#### **OPERATIVE DAY PRE-SURGERY**

- Confirm allocated drinks consumed as per instructions & document
- · Thirst and hunger sensation VAS score
- Blood samples on morning of surgery fasted (before consuming the intervention) if not done in POAC.
  - Fasting Glucose
  - Fasting Insulin (3 sample to be taken at 5 minute intervals)
  - Cortisol
  - o CRP
  - HbA1c (if not recently measured)
- Duration surgery (obtained from Theatreman system)
- Volume of blood loss
- Description of operation and type of primary analgesia obtained from Theatreman system or ERP Database
- Calories consumed

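### Hypo-/hyperglycaemia to the end of POD 1 is a named safety outcome, but no glucose is scheduled between the drink and POD 1 morning, so events in that interval are not systematically ascertained

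*Protocol*

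**What the plan says.** Section 5.4 (Secondary outcomes) names the safety outcome: "Adverse events i.e. aspiration and hypo- or hyperglycaemia (these are the only relevant safety assessments for these interventions"). It then sets the time frame: these events "will be assessed on the operative day for the former & up to the end of POD 1 for the latter", where the latter is hypo- or hyperglycaemia. The post-operative list in section 7.1 repeats the limit as "Adverse Events up to end POD 1".

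The drink comes early in that window. Section 5.3 tells both groups to "consume it between two and three hours before surgery, as per standard practice in the ERP".

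The blood sampling is in section 7.1:

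- Operative day, before surgery: "Blood samples on morning of surgery fasted (before consuming the intervention) if not done in POAC". Fasting glucose is on this list.
- After surgery: "Fasting insulin (3 samples to be taken at 5 minute intervals and glucose on the morning of POD 1, 2 and 3".
- Cortisol, listed separately: "Cortisol (at end of operation and at 24 hours").

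Section 7.1 also allows data to be taken from the anaesthetic chart, the operative note and the post-operative notes. Section 6.2 blinds patients only.

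**The concern.** The protocol regards abnormal glucose as one of the few safety questions these drinks raise, and it sets a window for it. The sampling schedule puts nothing in the first part of that window, which holds the hours after ingestion and the operation itself. The protocol's own rationale (section 4.1) expects the two drinks to differ in the initial glucose and insulin rise, in peak glucose and in duration of action. The next morning's fasting value says little about the first two.

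Without a scheduled value, an event in that interval enters the data only if someone had a clinical reason to test and wrote the result down. The count then depends partly on how often glucose was checked. What is at stake is the meaning of the between-arm comparison for this outcome: a low or equal count could not be told apart from little testing.

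**Working it through.** The protocol states no figure to reproduce, so the check is a count of scheduled glucose samples, in time order.

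1. **Pre-operative assessment clinic (7.1).** Fasting glucose for eligibility and baseline. This is before the drink.
2. **Morning of surgery (7.1).** Fasting glucose, before the drink, and only if the clinic sample was not taken. The footnote to the participant timeline (5.5) allows the baseline HOMA at either visit provided the patient is fasted. The operative-day HOMA mark is therefore a baseline, not a post-drink value.
3. **Drink (5.3).** Two to three hours before surgery.
4. **End of operation (7.1).** Cortisol only. Together with the pre-drink baseline, this accounts for the operative-day blood-sample mark in the timeline.
5. **Morning of POD 1 (7.1).** Fasting glucose and insulin, the first scheduled glucose after the drink.
6. **End of POD 1.** The safety window closes.

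The enhanced recovery appendix (10.1) lists no glucose monitoring that would fill the gap.

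Count of scheduled glucose values per patient:

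- between steps 3 and 5: **0**;
- between steps 3 and 6: **1**, the POD 1 morning sample.

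Length of the gap. The protocol gives no clock times, so these are assumptions: surgery starts between 08:30 and 14:00, the drink is taken 2 to 3 h earlier, and the POD 1 sample is drawn between 06:00 and 09:00.

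- Gap = 24 + sample time − (surgery start − lead time)
  - shortest: 24 + 6 − (14 − 2) = **18 h**
  - longest: 24 + 9 − (8.5 − 3) = **27.5 h**
- Window from drink to midnight at the end of POD 1 = 48 − (surgery start − lead time)
  - shortest: 48 − (14 − 2) = **36 h**
  - longest: 48 − (8.5 − 3) = **42.5 h**

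Effect of one added sample. With 40 patients, the scheduled post-drink values inside the window rise from 40 × 1 = 40 to 40 × 2 = 80 if all are obtained. The values in the gap rise from 0 to 40.

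The primary outcome uses the fasting baseline and the fasting POD 1 sample, both of which are scheduled. The gap does not touch it.

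**The case against.** The strongest reply is that section 5.4 lists these as adverse events, not as a glucose profile. Adverse events are collected to the end of POD 1, the charts and notes are read, and every patient has one scheduled glucose inside the window. This stands, so it would be wrong to call the interval unobserved. It is not systematically observed.

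A reader might go further and infer three things that the protocol does not support:

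- **That arterial-line patients will be tested often and others rarely.** Section 5.7 says only "Patients requiring admission to a higher level of care and therefore arterial line monitoring will be preferred due to the ease of blood sampling". It gives no testing frequency. Uneven testing between patients is plausible, but it is not stated.
- **That staff who know the arm decide when to test.** Section 5.3 says the research team knows the allocation, and section 6.2 blinds patients only. Nothing says that the anaesthetic or ward staff who would order a glucose know it. Differential testing by arm is possible, not shown. Section 6.2 defends open assessment by the objectivity of the primary end point, and that argument does not extend to an event that must first be looked for.
- **That no events would be reported as proof of safety.** The statistical section plans no formal safety conclusion.

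There are also fair points against the remedy. An end-of-operation sample comes two to three hours plus the length of the operation after the drink, so it misses the initial spike. Section 4.1 ties post-operative insulin resistance to surgical trauma and, in colorectal surgery, to operating time, so the value will also reflect the operation. These points limit the gain but do not remove it: every patient would have one value at a common point in the gap.

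Finally, this is a small pilot that the protocol calls low risk, it excludes known diabetes and impaired glucose tolerance, and it gives 47.5 g of carbohydrate in each arm. That bears on priority. The level that defines an event may be left to an analysis plan and is not part of this point. The sampling schedule is different, because no analysis can recover samples that were never taken.

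**Conclusion.** The point holds in a limited form. The outcome window in section 5.4 and the sampling lists in section 7.1 do not match: 0 scheduled glucose values between the drink and POD 1 morning, and 1 in the whole post-drink window. The count rests on the text alone. The duration of about 18 to 27.5 h, out of about 36 to 42.5 h, rests on the assumed clock times.

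In the gap, ascertainment depends on clinically prompted values in the chart or notes. It is not systematic and may vary between patients. It could vary by arm, but the protocol gives no evidence that it will, and the point should not be read as a finding of bias. The primary outcome is unaffected. This is a cheap improvement to a secondary safety outcome and no threat to the trial's main comparison.

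**What to change.** Add a glucose assay for every patient at the end-of-operation draw already scheduled for cortisol, and add it to the post-operative list in section 7.1. Compare the arms on the scheduled values, at end of operation and on POD 1 morning. List ad hoc values from charts and notes separately, as clinically detected events. A further glucose at the 24-hour cortisol draw would add little, since it falls after the gap and close to the POD 1 morning sample.

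If no sample is added, reconcile sections 5.4 and 7.1 in words: describe the outcome as clinically detected hypo- or hyperglycaemia only, and draw no between-arm safety conclusion from it.

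The cost is one extra assay per patient (40 in all), one more data field, and possibly one extra tube, because the blood sampling appendix lists the cortisol and glucose tubes separately. No extra venepuncture is needed. The report should state the limits of the added value: it does not capture the early post-drink peak, and it reflects surgical stress as well as the drink.
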